WHO	World Health Organization
WHO-DD	World Health Organization Drug Dictionary

1 Introduction

This statistical analysis plan (SAP) describes all planned analyses for the clinical study report(s) (CSR) of study CPDR001J2201, a randomized, open-label, phase II open platform study evaluating and safety of novel spartalizumab (PDR001) combinations in previously treated unresectable or metastatic melanoma.

The content of this SAP is based on protocol CPDR001J2201 version 01. All decisions regarding final analysis, as defined in the SAP document, have been made prior to database lock and unblinding of the study data.

1.1 Study design

This is a randomized, open-label, multi-center, two-part, open platform phase II study to assess the efficacy and safety of the anti-PD-1 antibody spartalizumab in combination with novel agents in previously treated unresectable or metastatic melanoma.

This study consists of two parts:

- Part 1: Selection phase (refer to [Section 1.1.1](#) for further details)
- Part 2 : Expansion phase (refer to [Section 1.1.2](#) for further details)

At any time during the study, subjects deemed eligible after the completion of screening procedures will be randomized into any of the combination arms open to enrolment (in either part 1 or part 2) for which the subject meets the eligibility criteria as described in Section 5 of the protocol using an Interactive Response Technology (IRT) system. Randomization will be stratified by baseline level of lactate dehydrogenase (LDH): baseline LDH \leq ULN (upper limit of normal) vs. baseline LDH $>$ ULN.

Crossover or re-randomization of subjects to other combination arms, including better performing arms, is not allowed.

Overall response rate (ORR), as assessed by local review of tumor response and using Response Evaluation Criteria in Solid Tumors (RECIST) 1.1 criteria, is the primary endpoint in this study. Duration of Response (DoR), as assessed by local review and using RECIST 1.1 criteria is the key secondary endpoint.

The primary analysis will be performed after all patients randomized in the expansion arm have been followed for at least 9 months or have discontinued study. Timing of the interim analyses is discussed further in [Section 1.1.3](#).

1.1.1 Study design: Part 1: Selection phase

The primary objective of part 1 is to evaluate the preliminary ORR of spartalizumab in combination with novel agents in patients with previously treated unresectable or metastatic melanoma.

As dose regimens for additional new combinations with spartalizumab become established, new combination arms will be added under the same master protocol through protocol amendments. A maximum of 10 arms may be active (open to enrolment) at any given time under this master protocol, and any arms active in part 1 will continue to be randomized with equal probability.

At each interim analysis, it will be determined which arm(s) (1) is declared efficacious and will be expanded to part 2, (2) will continue enrolment in part 1 (up to a maximum of 45 subjects enrolled in a given arm) or (3) will be dropped for futility, taking into account all available efficacy, safety and biomarker data. If a combination arm can be expanded to part 2, the exact sample size for part 2 will be determined at that time when the decision to expand this arm is taken (refer to Section 10.8 of the protocol for further details on sample size considerations). The timing of interim analyses and the criteria used for decision-making at each interim analysis are detailed in [Section 1.1.3](#) and Section 10 of the protocol.

Further discussion on the study design for part 1 can be found in Section 4.1 of the protocol.

1.1.2 Study design: Part 2: Expansion phase

The primary objective for part 2 is to further characterize ORR of spartalizumab in combination with novel agents with relevant preliminary activity, as determined in part 1, for patients with previously treated unresectable or metastatic melanoma.

Only combinations arms that have met the pre-specified criteria defined in [Section 1.1.3](#) and Section 10 of the protocol will be opened to enrollment in part 2.

Exact randomization strategies in the situation when there is one (or more) arms open for enrollment in part 2 and there are still arms open for enrollment in part 1 will be determined at the time of the selection of the arm that will be expanded in part 2. Four factors will be considered at the time of opening an arm in part 2 to determine the exact randomization strategy and those are the following:

- 1) Number of subjects enrolled in part 1 for the arm that will graduate to part 2
- 2) Number of subjects that will need to be enrolled in part 2 to have sufficient predictive power and alpha control
- 3) Observed effect size for the arm that will graduate to part 2
- 4) Observed effect size of other arms which are open for enrolment in part 1

[figure not shown]
Further discussion on the study design for part 2 can be found in Section 4.1 of the protocol.

1.1.3 Timing of interim analyses and design adaptations

The first interim analysis will be conducted in part 1 after approximately 10 subjects have been enrolled in each of the first three arms and have completed the second post-baseline tumor assessment or have discontinued study prior to completing the second post-baseline tumor assessment. The requirement to have at least 10 subjects in each arm is based on simulations showing that 10 is the minimal number of subjects to be able to declare futility as per decision rules presented below and also in Section 10.4.2 of the protocol. If more combination arms are added to the study via future protocol amendments, those combination arms would also have their 1st interim analysis after approximately 10 subjects have been enrolled. Timing of subsequent interim analyses for part 1 and statistical thresholds are further discussed in Section 4.2 of the protocol and Section 10.4.2 of the protocol, respectively. [13621010910464462Statistical_hypo](#)No interim analysis is planned for part 2.

Figure 1-1 presents pre-specified criteria for decision-making in the selection phase.

Figure 1-1 Pre-specified criteria for decision making at each decision point (interim analysis) in part 1 to determine expansion in part 2 or drop of a combination arm

[figure not shown]
1.2 Study objectives and endpoints

Objectives and related endpoints are described in Table 1-1 below.

Table 1-1 Objectives and related endpoints

Primary objective	Endpoint
To evaluate the efficacy of each combination arm, as measured by confirmed objective response rate (ORR)	Confirmed ORR using RECIST v1.1, per local assessment
Key secondary objective	Endpoint
To evaluate the efficacy of each combination arm in terms of duration of response (DoR)	DoR using RECIST v1.1, per local assessment
Other secondary objectives	Endpoint
To evaluate the efficacy of each combination arm as measured by progression-free survival (PFS) and disease control rate (DCR)	PFS and DCR, assessed using RECIST v1.1, per local assessment
To evaluate the overall survival (OS) of each combination arm	Overall survival (OS)
To characterize the safety and tolerability of each combination arm	Safety : Incidence and severity of adverse event (AE) including changes in laboratory values, vital signs and cardiac assessment. Tolerability : Dose interruptions, reductions, and permanent discontinuations of study treatments

To characterize the prevalence and incidence of immunogenicity of spartalizumab, LAG525 and canakinumab in each combination arm	Anti-drug antibodies (ADA) prevalence at baseline and ADA incidence on treatment
To evaluate changes in levels and phenotype of T cell populations in the tumor and tumor microenvironment after treatment with combination therapies	Proportion of subjects with a favorable biomarker profile (pFBP), as defined by changes in numbers of cells expressing the CD8 ⁺ T cell marker and/or T cell activation marker(s), T cell clonality and/or gene expression in tumor biopsy samples collected at baseline (screening) and compared to on treatment (3-4 weeks) samples

2 Statistical methods

2.1 Data analysis general information

All analysis will be performed by Novartis and/or a designated CRO. SAS version 9.4 or later software will be used to perform all data analyses and to generate tables, figures and listings. Analysis using Rshiny apps might also be used as needed.

Data included in the analysis

The analysis cut-off date for the primary analysis of study data will be established after all randomized patients in the expansion arm have either completed nine months of follow-up or have discontinued study. For the selection phase, interim analyses will be conducted once the 1st 10 subjects have been enrolled in each of the 1st three arms and then conducted approximately every 20 weeks thereafter. No formal interim analysis for efficacy will be conducted for combination arms in the expansion phase.

For each of the analyses, all statistical analyses will be performed using all data collected in the database up to the data cut-off date. All data with an assessment date or event start date (e.g. vital sign assessment date or start date of an adverse event) prior to or on the cut-off date will be included in the analysis. Any data collected beyond the cut-off date will not be included in the analysis and will not be used for any derivations.

All events with start date before or on the cut-off date and end date after the cut-off date will be reported as 'ongoing'. The same rule will be applied to events starting before or on the cut-off date and not having documented end date. This approach applies, in particular, to adverse event and concomitant medication reports. For these cases, the end date will not be imputed and therefore will not appear in the listings.

The analysis cutoff date for the final analysis of study data will be established at the end of the study defined as the earliest occurrence of one of the following:

- All subjects have died or discontinued from the study
- Another clinical study (i.e. rollover study) becomes available that can continue to provide the appropriate combination treatment in this subject population and all subjects ongoing are eligible to be transferred to that clinical study
- 52 weeks after data-cut for primary CSR. For subjects still receiving study treatment at the time of end of study, every effort will be made to continue provision of study treatment outside this study through an alternative setting (e.g. post-trial access programs) to subjects who in the opinion of the investigator are still deriving clinical benefit.

The timing of primary and final analyses will be updated, should new arms be added through protocol amendment or if more than one arm is expanded to the expansion phase.

General analysis conventions

Pooling of centers: Unless specified otherwise, data from all study centers will be pooled for the analysis. Due to expected small number of patients enrolled at each centers, no center effect will be assessed.

Qualitative data (e.g., gender, race, etc.) will be summarized by means of contingency tables; a missing category will be included as applicable. Percentages will be calculated using the number of patients in the relevant population or subgroup as the denominator.

Quantitative data (e.g., age, body weight, etc.) will be summarized by appropriate descriptive statistics (i.e. mean, standard deviation, median, minimum, and maximum).

2.1.1 General definitions

Investigational drug and study treatment

Investigational drug can refer to either PDR001 or any of the novel agents.

Study treatment will refer to PDR001 in combination with any of the novel agents.

The term investigational treatment may also be referred to as **study treatment** which is used throughout this document.

Date of first administration of investigational drug

The date of first administration of investigational drug is defined as the first date when a non-zero dose of investigational drug is administered and recorded on the Dosage Administration Record (DAR) Electronic Case Report Form (eCRF). The date of first administration of study drug will also be referred as start of investigational drug.

Date of last administration of investigational drug

The date of last administration of investigational drug is defined as the last date when a nonzero dose of investigational drug is administered and recorded on DAR eCRF. The date of last administration of investigational drug will also be referred as end of investigational drug.

Date of first administration of study treatment

The date of first administration of study treatment is derived as the first date when a nonzero dose of any component of study treatment was administered as per the Dosage Administration (e)CRF. (Example: if 1st dose of PDR001 is administered on 28-Jul-2018, and 1st dose of combination partner is administered on 26-Jul-2018, then the date of first administration of study treatment is on 26-Jul-2018). The date of first administration of study treatment will also be referred as *start of study treatment*.

Date of last administration of study treatment

The date of last administration of study treatment is derived as the last date when a nonzero dose of any component of study treatment was administered as per Dose Administration (e)CRF. (Example: if the last PDR001 dose is administered on 26-Jul-2019, and the last dose of a combination partner is administered on 28-Jul-2019, then the date of last administration of study treatment is on 28-Jul-2019).

Study day

The study day, describes the day of the event or assessment date, relative to the reference start date.

The study day is defined as:

- The date of the event (visit date, onset date of an event, assessment date etc.) – reference start date + 1 if event is on or after the reference start date;
- The date of the event (visit date, onset date of an event, assessment date etc.) – reference start date if event precedes the reference start date.

The reference start date for safety assessments (e.g. adverse event onset, laboratory abnormality occurrence, vital sign measurement, dose interruption, █ etc.) is the start of study treatment.

The reference start date for all other, non-safety assessments (i.e., tumor assessment, survival time, disease progression, tumor response, and Eastern Cooperative Oncology Group [ECOG]) performance status is the date of randomization.

The study day will be displayed in the data listings. If an event starts before the reference start date, the study day displayed on the listing will be negative.

Time unit

A year length is defined as 365.25 days. A month length is 30.4375 days (365.25/12). If duration is reported in months, duration in days will be divided by 30.4375. If duration is reported in years, duration in days will be divided by 365.25.

Baseline

For efficacy evaluations, the last non-missing assessment, including unscheduled assessments on or before the date of randomization is taken as “baseline” value or “baseline” assessment. In the context of baseline definition, the efficacy evaluations also include performance status.

For safety evaluations, the last available assessment is on or before the date of start of study treatment is taken or “baseline” assessment.

In case time of assessment and time of treatment start is captured (e.g. pre-dose ECG), the last available assessment before the treatment start date/time is used for baseline.

For safety parameters (e.g ECGs or vital signs), where study requires multiple replicates per time point, the average of these measurements would be calculated for baseline (if not already available in the database).

In rare cases where multiple measurements meet the baseline definition, with no further flag or label that can identify the chronological order, then the following rule should be applied: If values are from central and local laboratories, the value from central assessment should be considered as baseline. If multiple values are from the same laboratory (local or central) or collected for ECGs or vital signs, then the last value should be considered as baseline.

If patients have no value as defined above, the baseline result will be missing.

On-treatment assessment/event and observation periods

For adverse event reporting the overall observation period will be divided into three mutually exclusive segments:

1. ***pre-treatment period***: from day of patient’s informed consent to the day before first administration of study treatment
2. ***on-treatment period***: from date of first administration of study treatment to 30 days after date of last actual administration of any study treatment (including start and stop date)
3. ***post-treatment period***: starting at day 31 after last administration of study treatment.

Notes:

- If data on clock time is available in the clinical database (e.g. for time of blood/urine sample taken, ECG performed, etc. and first study treatment administration), a more precise distinction between pre-treatment and on-treatment periods is encouraged to be used.
- If dates are incomplete in a way that clear assignment to pre-, on-, post-treatment period cannot be made, then the respective data will be assigned to the on-treatment period.

Safety summaries (tables, figures) include only data from the on-treatment period with the exception of baseline data which will also be summarized where appropriate (e.g. change from baseline summaries). In addition, a separate summary for death including on treatment and post treatment deaths will be provided. In particular, summary tables for adverse events (AEs) will summarize only on-treatment events, with a start date during the on-treatment period (**treatment-emergent** AEs). However, all safety data (including those from the post-treatment period) will be listed and those collected during the pre-treatment and post-treatment period will be flagged.

Additional summaries will be displayed to report deaths, all AEs, AEs related to study treatment, all Serious Adverse Events (SAEs) and SAEs related to study treatment collected up to 150 days after last administration of PDR001.

Note: If a patient starts a post-treatment antineoplastic therapy after the last administration of study treatment, only adverse events suspected to be related to study treatment will be collected up to 150 days after discontinuation of PDR001. All AEs/ all SAEs are planning to be reported up to 150 days after discontinuation of PDR001 acknowledging that complete collection of data may not be feasible for each patient.

However, all safety data (including those from the post-treatment period) will be listed and those collected during the pre-treatment and post-treatment period will be flagged.

Windows for multiple assessments

In order to summarize performance status (ECOG), [REDACTED] laboratory, and vital signs collected over time (including unscheduled visits), the assessments will be time slotted. The following general rule will be applied in creating the assessment windows: If more than one assessment is done within the same time window, the assessment performed closest to the target date will be used. If 2 assessments within a time window are equidistant from the target date, then the earlier of the 2 assessments will be used. If multiple assessments on the same date then the worst case will be used. Data from all assessments (scheduled and unscheduled), including multiple assessments, will be listed.

Table 2-1 Time window for ECOG PS assessments

Assessment	Target day of assessment	Time Interval
Baseline		≤ Day 1
Cycle 2 Day 1	29	Day 15 to day 42
Cycle 3 Day 1	57	Day 43 to day 70
Cycle 4 Day 1	85	Day 71 to day 98
Cycle k Day 1 (k≥5)	d=(k-1)*28+1	Day d-14 to day d+13
End of Treatment		Assessment taken at the end of treatment visit
30-day safety follow-up	Post treatment study day 30	Assessment taken at the 30-day safety follow-up visit

Table 2-2 Time window for Laboratory assessments

Assessment	Target day of assessment	Time Interval
Baseline		≤ Day 1
Cycle 1 Day 15	15	Day 2 to day 21
Cycle 2 Day 1	29	Day 22 to day 42
Cycle 3 Day 1	57	Day 43 to day 63
Cycle 3 Day 15	71	Day 64 to day 77
Cycle 4 Day 1	85	Day 78 to day 98
Cycle k Day 1 (k≥5)	d=(k-1)*28+1	Day d-14 to day d+13
End of Treatment		Assessment taken at the end of treatment visit
30-day safety follow-up	Post treatment study day 30	Assessment taken at the 30-day safety follow-up visit

Last contact date

The last contact date will be derived for patients not known to have died at the analysis cut-off using the last complete date among the following:

Table 2-3 Last contact date data sources

Source data	Conditions
Date of Randomization	No Condition
Last contact date/last date patient was known to be alive from Survival Follow-up page	Patient status is reported to be alive, lost to follow-up or unknown
Start/End dates from further antineoplastic therapy	Non-missing medication/procedure term.
Start/End dates from drug administration record	Non-missing dose. Doses of 0 are allowed.
End of treatment date from end of treatment page	No condition.
Tumor (RECIST) assessment date.	Evaluation is marked as 'done'.
Verification for treatment beyond RECIST1.1 PD	At least one non missing parameter value
Laboratory ████ collection dates	Sample collection marked as 'done'.
Vital signs date	At least one non-missing parameter value
Performance Status date	Non-missing performance status
Start/End dates of AE	Non-missing verbatim term

The last contact date is defined as the latest complete date from the above list on or before the data cut-off date. The cut-off date will not be used for last contact date, unless the patient was seen or contacted on that date. No date post cut-off date will be used. Completely imputed dates (e.g. the analysis cut-off date programmatically imputed to replace the missing end date of a dose administration record) will not be used to derive the last contact date. Partial date imputation is allowed for event (death)/censoring is coming from 'Survival information' eCRF.

The last contact date will be used for censoring of patients in the analysis of overall survival.

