2.8.1 Adverse events (AEs)

AE summaries will include all AEs occurring during on treatment period. Additional summaries will be displayed to report all AEs, AEs related to study treatment, all SAEs and SAEs related to study treatment collected up to 150 days after last administration of PDR001. All AEs collected in the AE (e)CRF page will be listed along with the information collected on those AEs e.g. AE relationship to study drug, AE outcome etc. AEs with start date outside of on-treatment period will be flagged in the listings.

AEs will be summarized by number and percentage of subjects having at least one AE, having at least one AE in each primary system organ class (SOC) and for each preferred term (PT) using MedDRA coding. A subject with multiple occurrences of an AE will be counted only once in the respective AE category. A subject with multiple Common Terminology Criteria for Adverse Events (CTCAE) grades for the same preferred term will be summarized under the maximum CTCAE grade recorded for the event. AE with missing CTCAE grade will be included in the 'All grades' column of the summary tables.

In AE summaries, the primary system organ class will be presented alphabetically and the preferred terms will be sorted within primary SOC in descending frequency. The sort order for the preferred term will be based on their frequency in the total column.

The following adverse event summaries will be produced by treatment arm; overview of adverse events and deaths (number and % of subjects who died, with any AE, any SAE, any dose reductions/interruptions, leading to treatment discontinuation), AEs by SOC and PT, summarized by relationship (all AEs and AEs related to study treatment), seriousness (SAEs and non-SAEs), leading to treatment discontinuation, leading to dose interruption/adjustment, requiring additional therapy, requiring immunosuppressive medication and leading to fatal outcome. In addition, a summary of serious adverse events with number of occurrences will be

produced (an occurrence is defined as >1 day between start and prior end date of record of same preferred term).

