2.8.1.1 Adverse events of special interest / grouping of AEs

Adverse events of special interest (AESI) during the on-treatment period will be tabulated. The list of AESI will also include relevant events for spartalizumab, and the novel agents.

Data analysis of AESIs

An adverse event of special interest (AESI) is a grouping of adverse events that are of scientific and medical concern specific to compound PDR001, the individual novel agents, as well as combination specific AESIs (PDR001 + novel agent). These groupings are defined using MedDRA terms, SMQs (standardized MedDRA queries), HGLTs (high level group terms), HLT (high level terms) and PTs (preferred terms). Customized SMQs (Novartis MedDRA queries, NMQ) may also be used. A NMQ is a customized group of search terms which defines a medical concept for which there is no official SMQ available or the available SMQ does not completely fit the need. It may include a combination of single terms and/or an existing SMQ, narrow or broad. All AESI terms for the individual compounds as well as for combination specific AESIs are captured in the case retrieval strategy (CRS).

For each specified AESI, number and percentage of patients with at least one event of the AESI occurring during on treatment period will be summarized.

Summaries of these AESIs will be provided by treatment arm, (specifying grade, SAE, relationship, leading to treatment discontinuation, leading to dose adjustment/interruption, hospitalization, death, requiring immunosuppressive medication etc.). If sufficient number of events occurred, analysis of time to first occurrence will be applied.

Additional summaries will be provided to report all AESIs, AESIs related to study treatment, all serious AESIs and serious AESIs related to study treatment collected during the on-treatment period and up to 150 days after last administration of PDR001.

A listing of all grouping levels down to the MedDRA preferred terms used to define each AESI will be generated. This listing should be included in section 16 of CSR.

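### The 150-day all-cause AE, SAE and AESI percentages cover time after new anticancer therapy, when only related events are collected, so they are understated and not like-for-like with the related-event tables

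*SAP*

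**What the plan says.** SAP section 2.1.1 limits the main tables to the on-treatment period, which ends 30 days after the last dose: "summary tables for adverse events (AEs) will summarize only on-treatment events, with a start date during the on-treatment period". It then adds an extended set: "Additional summaries will be displayed to report deaths, all AEs, AEs related to study treatment, all Serious Adverse Events (SAEs"), continuing to "SAEs related to study treatment collected up to 150 days after last administration of PDR001".

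A note in the same section changes what is collected inside that window. The trigger is "If a patient starts a post-treatment antineoplastic therapy after the last administration of study treatment"; from then on "only adverse events suspected to be related to study treatment will be collected up to 150 days after discontinuation of PDR001". The next sentence keeps the full window anyway: "All AEs/ all SAEs are planning to be reported up to 150 days after discontinuation of PDR001 acknowledging that complete collection of data" might not be achievable for every patient.

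Later sections repeat the extended summaries with no cut at new therapy. Section 2.8.1 has "Additional summaries will be displayed to report all AEs, AEs related to study treatment, all SAEs and SAEs related to study treatment" and section 2.8.1.1 has "Additional summaries will be provided to report all AESIs, AESIs related to study treatment, all serious AESIs and serious AESIs related to study treatment". The Arm 1A SAP, section 2.1.1, defines an extended follow-up of 150 days after the last PDR001/LAG525 dose, again with no cut. It takes the general definitions it does not replace from the main SAP, and its sections 2.8.1 and 2.8.1.1 send the AE and AESI tables to that extended window.

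The results are numbers and percentages of subjects, each subject counted once per category (section 2.8.1), on the safety set (section 2.8), with the relevant population as denominator (section 2.1).

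**The concern.** The content of the AE record changes partway through the window, at a point that differs by patient. Before new therapy, related and unrelated events are both recorded; afterwards only related ones are. A patient who has switched stays in the denominator of the all-cause tables as if still fully observed, so an unrelated late event in that patient appears as no event.

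The acknowledgement in section 2.1.1 describes the gap as a matter of feasibility in individual patients. The sentence before it is a rule that drops one class of event after a defined trigger. No cut, time at risk, count of affected patients or sensitivity table follows from it.

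At stake is the description of late toxicity, which is the purpose of the 150-day tables. The all-cause tables will read low, and anyone setting them beside the related-event tables will be comparing two different observation periods.

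**Working it through.** The SAP gives no figure on this point, so there is none to reproduce.

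**Inputs from the SAP.** The window is 150 days after the last PDR001 dose. The on-treatment period ends 30 days after the last dose. Taking the last PDR001 dose as the last study dose, the late part is 150 − 30 = 120 days.

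**Inputs assumed, because the SAP does not give them.** These are the share f of patients starting new therapy in the late part; the fraction t of the 120 days elapsed at that start; the late risks U (unrelated) and R (related); constant hazards; and, in step 3, time on treatment.

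**1. Direction (needs no rates).** Let A be the subjects with a related event anywhere in the window. Let B be those with no related event but an unrelated one before new therapy. Let C be those whose only events are unrelated and fall after new therapy.
- Complete collection would give an all-cause count of A + B + C; the planned table gives A + B.
- The related count is A in both cases.
- So observed all-cause ≤ true, and A/(A+B) ≥ A/(A+B+C). Equality holds only if C is empty.

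**2. Illustration for days 31 to 150.** With hu = −ln(1−U) and hr = −ln(1−R):

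observed all-cause = (1−f)[1−exp(−(hu+hr))] + f[1−exp(−(hu·t+hr))]

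For U = 30% and R = 10%, hu = 0.357 and hr = 0.105. Complete collection gives 1 − 0.7×0.9 = 37.0%.

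| f | t | Observed all-cause | Related ÷ all-cause |
|---|---|---|---|
| 0 | – | 37.0% | 27.0% |
| 20% | 0.25 | 33.1% | 30.2% |
| 40% | 0.25 | 29.3% | 34.2% |
| 60% | 0.25 | 25.4% | 39.4% |
| 40% | 0 | 26.2% | 38.2% |
| 40% | 0.5 | 32.1% | 31.2% |

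For U = R = 10%, f = 40% and t = 0.25, all-cause falls from 19.0% to 16.3% and the ratio rises from 52.6% to 61.2%.

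**3. Dilution in the tables as planned.** Suppose half the patients switch at day 45.
- All-cause collection over days 31 to 150 alone covers (0.5×120 + 0.5×15)/120 = 56% of patient-days.
- The planned tables also hold on-treatment time. Assuming 84 days from first to last dose, the span is 84 + 150 = 234 days. The loss is 0.5×(150−45) = 52.5 days, so coverage is 181.5/234 = 78%.
- With 70% switching at day 31, the loss is 0.7×119 = 83.3 days and coverage is 64%. With 30% switching at day 60, the loss is 0.3×90 = 27 days and coverage is 88%.

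A subject who already had an on-treatment event in a given row is unaffected in that row. The any-AE row should therefore move little; SAE, AESI and preferred-term rows are more exposed.

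**4. Two candidate remedies, at U = 30%, R = 10%, f = 40%, t = 0.25.**
- *Cut only the all-cause column at new therapy.* This gives 0.6×0.370 + 0.4×[1−exp(−0.462×0.25)] = 26.6%. It is further below 37.0% than the 29.3% in the plan, and the ratio rises to 10/26.6 = 37.6%. This makes matters worse.
- *Cut both columns at new therapy.* Related becomes 0.6×0.10 + 0.4×[1−exp(−0.105×0.25)] = 7.04%, and the ratio is 7.04/26.56 = 26.5%, close to 27.0%. Event-free time to the cut is 0.222/0.462 + 0.0436/0.462 = 0.575 windows per patient. The all-cause rate is then 0.2656/0.575 = 0.462 per window, the complete-collection value.

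**The case against.** The strongest reply is that the SAP states the limitation where it defines the summaries, and section 2.4.2 does the same for concomitant medications. These are additional tables, and all safety data are listed with post-treatment events flagged. The collection rule itself normally belongs to the protocol. It can also be argued that all-cause events after a switch include toxicity of the next therapy, which is not the target for study-drug safety.

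Much of this stands. The gap is acknowledged, not hidden, and stopping collection may be reasonable. It does not answer the analysis point: the percentages still treat switched patients as observed for unrelated events. If post-switch unrelated events are off target, that is a reason to end the all-cause window at the switch.

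Three stronger readings might be inferred, and the document does not support them.
- *The main safety tables are biased.* They stop 30 days after the last dose, so only patients who start new therapy within those 30 days are touched.
- *The SAP reports an inflated related share.* No such share is a planned output; the distortion appears only when the two sets of tables are read together.
- *A between-arm safety comparison is invalidated.* No between-arm safety test is planned, and Arm 1A is analysed alone. Arms that switch earlier would lose more all-cause events, but that is a caution for informal reading only.

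**Conclusion.** The point holds for the additional 150-day summaries of all-cause AEs, SAEs and AESIs, in the main SAP and for Arm 1A. The late all-cause percentages are understated whenever a switched patient's only event in a row is an uncollected unrelated one, and they are not like-for-like with the related-event percentages. The direction follows from the collection rule, provided related events are fully collected and attribution does not change after the switch.

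The size is unknown, because the SAP gives neither the share of patients starting new therapy in the window nor any event rate. With assumed late risks of 30% and 10%, and 20% to 60% of patients switching a quarter of the way through, the late all-cause figure is 33.1% to 25.4% instead of 37.0%. The shortfall in the planned tables would be smaller, since they also count on-treatment events. Deaths are not named in the collection restriction and are not affected. It is a limited reporting defect, worth correcting because the remedy is modest.

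**What to change.** For the extended window, in both the main and Arm 1A SAPs:

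- Report all-cause and related AEs, SAEs and AESIs with the same cut: the earlier of 150 days and the start of new antineoplastic therapy. Give the number of patients and exposure-adjusted incidence, with patient-time at risk to that cut.
- Report related events and deaths to the full 150 days in a separate, labelled table.
- State how many patients started new therapy within the window.
- Do not cut only the all-cause percentage column; as shown above, that enlarges the distortion.

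The start date of further antineoplastic therapy is already collected (section 2.1.1, Table 2-3) and already used for censoring DoR and PFS (sections 2.6.3 and 2.7.1). The cost is one extra date cut, one extra table and the time-at-risk derivation. The exposure-adjusted rates assume that starting new therapy is not informative for event risk, which may not hold and should be stated in a footnote.
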